ATC	anatomical therapeutic chemical
AF	autofluorescence
BCVA	best corrected visual acuity
BIIB111	timrepigene emparvovec
CHM	choroideremia
CI	confidence interval
CM	concomitant medication
CSR	clinical study report
eCRF	electronic case report form
ELISA	enzyme-linked immunosorbent assay
ELISpot	enzyme-linked immunospot
ERM	epiretinal membrane
ET	early termination
ETDRS	Early Treatment Diabetic Retinopathy Study
FC	foveal center
IOP	intraocular pressure
LOCF	last observation carried forward
LOCS	lens opacities classification system
MAIA	Macular Integrity Assessment
MedDRA	Medical Dictionary for Regulatory Activities
MH	macular hole
Nabs	neutralizing timrepigene emparvovec antibodies
OD	oculus dextrus (right eye)
OU	oculus uterque (both eyes)
OS	oculus sinister (left eye)
P05	fifth percentile
P95	ninety fifth percentile
PT	preferred term
Q1	first quartile
Q3	third quartile
REP1	rab escort protein 1
RPE	retinal pigment epithelium
SAE	serious adverse event
SAP	statistical analysis plan
SAS	statistical analysis system
SD	standard deviation
SD-OCT	spectral domain optical coherence tomography
SE1	study eye 1
SE2	study eye 2
SFU	spot forming units
SOC	system organ class
SRF	subretinal fluid

TEAE	treatment-emergent adverse event
USAN	United States adopted name
vg	vector genomes
VMT	vitreomacular traction
WHODD	World Health Organisation drug dictionary

1 Introduction

This document presents the statistical analysis plan (SAP) for the NightstaRx-sponsored Protocol No. 273CH203 / NSR-REP-02: An Open-Label Safety Study of Retinal Gene Therapy for Choroideremia with Bilateral, Sequential Administration of Adeno-Associated Viral Vector (AAV2) Encoding Rab Escort Protein 1 (REP1) (GEMINI Study).

AAV2-REP1 is denoted hereafter by the USAN timrepigene emparvovec (BIIB111).

This analysis plan is based on the final protocol dated 30 Oct 2019, incorporating the following versions/ amendments:

- Original protocol, dated 4 Jul 2017
- Amendment No. 1, version 2, dated 17 May 2018
- Amendment No. 2, version 3, dated 04 Feb 2019 (internal amendment only)
- Amendment No. 2.1, version 3.1, dated 19 Feb 2019
- Amendment No. 3, version 4, dated 30 Oct 2019

The SAP provides the description of the final analyses for the generation of the clinical study report.

2 Study Objectives and Endpoints

2.1 Objective

The objective of the study is to evaluate the safety of bilateral, sequential sub-retinal administration of a single dose of timrepigene emparvovec in adult male subjects with choroideremia (CHM).

2.2 Endpoints

2.2.1 Safety Endpoints

The safety of bilateral administration of timrepigene emparvovec will be evaluated with the following safety measures:

- Best Corrected Visual Acuity (BCVA) as measured by the Early Treatment of Diabetic Retinopathy Study (ETDRS) chart
- Ophthalmic examination assessments (including intraocular pressure [IOP], slit lamp examination, lens opacity grading and dilated ophthalmoscopy)
- Spectral domain optical coherence tomography (SD-OCT)
- Fundus autofluorescence
- Fundus photography
- Microperimetry
- Adverse Event (AE) reporting
- Vector shedding post-treatment
- Immunogenicity sampling post-treatment
- Vital signs

2.2.2 Secondary Efficacy Endpoints

- Change from Baseline in BCVA as measured by the ETDRS chart
- Change from Baseline in autofluorescence
- Change from Baseline in SD-OCT
- Change from Baseline in microperimetry

[figure not shown]
3 Study Design

3.1 Discussion of Study Design

This is a Phase 2, multi-centre, open-label, prospective, 2-period, bilateral interventional safety study of timrepigene emparvovec in adult male subjects with genetically confirmed CHM.

The study will consist of a Screening Period followed by 2 treatment periods (Period 1 and Period 2) with up to 9 visits per treatment period. A second baseline visit prior to surgery of Study Eye 2 (SE2) (Period 2, Visit 1) may be required. A study schematic is presented in [Figure 1](#).

Figure 1 Overall Study Schematic

During the Screening Period, subjects will be assessed for eligibility of both eyes. The investigator will assign the order in which the eyes are treated (i.e., study eye 1 [SE1] period 1 and study eye 2 [SE2] period 2, respectively) with a number assigned to each eye. This will be done in collaboration with the subject; however, the worse eye will generally be selected for first treatment. The estimated target interval between the surgical procedures of SE1 and SE2 will be determined at the Screening Visit.

Each study eye will be followed for at least 12 months post-treatment, for up to 9 visits per treatment period: Visit 1 (Day 0, Injection Day Visit); Visit 2 (Day 1, post-operative follow up visit); Visit 3 (Day 3 + 2 Days); Visit 4 (Day 7 -1/+2 Days); Visit 5 (Day 14 ± 3 Days); Visit 6 (Month 1 ± 7 Days); Visit 7 (Month 3 ± 14 Days); Visit 8 (Month 6 ± 14 Days) and Visit 9 (Month 12 ± 14 Days).

The interval between SE1 and SE2 treatment is expected to vary among subjects from weeks to many months. While the interval will be decided on a case-by-case basis, an effort will be made to schedule varying treatment intervals in order to better characterise the immunological and safety profile of sequential treatment administration. Thus, approximately 20 subjects each will be treated with a short- (<6 month), medium- (6-12 months), or long- (>12 month) surgery window between treatment of the first and second eye. Because the timing of the second surgery visit (Period 2, Visit 1) will vary among subjects, the duration of study Period 1 will also be variable.

All baseline ophthalmic assessments must be conducted within 3 months prior to SE2 surgery (Period 2, Visit 1). If these assessments are not available within the required timeframe, a Baseline Visit must be added to collect current baseline data on SE2. If, at that time, BCVA in SE2 is <34 ETDRS letters, surgery may be performed when, in the opinion of the

investigator and after consultation with the sponsor: 1) the subject is found eligible by all other inclusion and exclusion criteria, and 2) the subject is considered an appropriate candidate who has potentially modifiable disease.

The post-operative outcome and visual function of SE1 will inform the scheduling of Period 2. Signs of post-operative inflammation or other post-operative sequelae, as judged by the investigator, should be resolved in SE1 for the subject to continue to Period 2. After comprehensive evaluation of all safety assessments and visual functional tests of SE1 and SE2, the Investigator will determine the eligibility of the subject and decide the appropriate time to schedule SE2, Visit 1.

Subjects who develop cataracts may undergo cataract surgery if deemed clinically necessary. If cataract surgery is performed, it should be carried out at least 4 weeks before Month 12 (Visit 9) for the respective eye. The cataract surgery timing must be discussed with the medical monitor prior to the procedure.

Subjects Previously Treated with Timrepigene Emparvovec

Subjects who have previously participated in a clinical trial of AAV2-REP1 for the treatment of CHM and have received AAV2-REP1 in one eye may be eligible for participation in this study. In these cases, only the subject's untreated eye will be assessed for eligibility. Following the Screening Visit and determination of eligibility, the subject will move directly into Period 2 for treatment of SE2.

3.2 Study Treatment

Eligible subjects will undergo vitrectomy and retinal detachment in each eye. At Period 1, Visit 1 (Day 0, the Injection Day Visit for SE1), subjects will receive in SE1 a sub-retinal injection of up to 0.1 mL of study drug containing 1×10^{11} timrepigene emparvovec vg. At Period 2, Visit 1 (Day 0, the Injection Day Visit for SE2), subjects will receive in SE2 up to 0.1 mL of timrepigene emparvovec via sub-retinal injection.

3.3 Study Schedule

At Period 1, Visit 1 (Day 0, Injection Day Visit for SE1), subjects will undergo a vitrectomy with retinal detachment and receive a sub-retinal injection of timrepigene emparvovec in SE1. Visits 2-9 will then be conducted according to the Schedule of Study Procedures, unless Period 2 commences during the time of follow-up for SE1; in which case, the study visits will continue following the schedule for SE2. Ophthalmic assessments during Period 1, Visits 2-9 will be performed on both eyes.

At Period 2, Visit 1 (Day 0, Injection Day Visit for SE2), subjects will undergo a vitrectomy with retinal detachment and sub-retinal injection of timrepigene emparvovec in the contralateral, untreated eye (SE2). Post-treatment, subjects will no longer follow the Period 1 visit schedule, but will instead attend Period 2, Visits 2-9 according to the Schedule of Study Procedures. Ophthalmic assessments scheduled for Period 2, Visits 2-9 will be performed on both eyes.

Study data will thus be collected for both eyes in each subject. Subjects will be assessed for safety and efficacy throughout the study, as outlined in the Schedule of Study Procedures ([Section 7.2](#)).

A subject is considered to have completed the study if he completes Period 2, Visit 9 (Month 12). The end of the trial is the date the last subject completes Period 2, Visit 9 (Month 12) assessments (or early termination [ET] assessments in the event of premature discontinuation) or the date of last data collection if the last subject is lost to follow-up.

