8.3 Subject Withdrawal Criteria

Each subject has the right to withdraw from the study at any time without prejudice. In addition, the Investigator may discontinue a subject from the study at any time if the Investigator considers it necessary for any reason, including:

- Significant protocol deviation
- Significant non-compliance with study requirements
- AE which results in an inability to continue to comply with study assessments
- Lost to follow up
- Other (to be specified on the electronic case report form [eCRF]).
 - If severe ocular inflammation (e.g. endophthalmitis) or any other post-operative sequela that is unresponsive to treatment occurs in SE1, the second eye should not be treated. However, Period 1 should be continued for monitoring of safety for the duration of the study.
 - At the discretion of the Investigator, if a persistent post-operative complication or poor visual function outcome presents post-operatively in SE1, the second eye may not be treated. However, Period 1 should be continued for monitoring of safety for the duration of the study.

In the event that a subject discontinues the study, the reason for withdrawal is to be recorded in the eCRF, and the site should use every reasonable effort to ensure that an end of trial (ET) Visit is conducted as outlined in the Schedule of Study Procedures ([Table 1](#)). If the subject is withdrawn due to an AE, the Investigator will arrange for follow-up until the event has resolved, subsided, stabilised, or the subject withdraws consent or is lost to follow-up. For subjects who withdraw consent, data will be collected through their last available study visit. Subjects withdrawn from the study may possibly be replaced. Subjects who withdraw from the study must undergo the ET Visit assessments. See [Table 1](#).

Withdrawal from the study will not result in the exclusion of a subject's data acquired up to the point of withdrawal.

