11.3 Stopping Criteria

- Severe ocular inflammation (e.g. endophthalmitis) that is unresponsive to treatment should result in the affected subject not being treated in the second eye. However, the subject will continue to be followed for safety for the duration of the study.
- At the request of the DMC, the trial may be stopped based on specific safety concerns (i.e., SUSARs), not defined in the Investigator's Brochure (Section 6.3).
- The study may be discontinued if the Sponsor deems it necessary for medical, safety, regulatory, business, or other reasons consistent with applicable laws or regulations.

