13.6.7 Adverse Events

AEs will be coded using the Medical Dictionary for Regulatory Affairs, version 21.0 or higher. Events will be summarised by system organ class and preferred term and eye. The number of eyes with an AE, as well as the number of events, will be summarised, by period and eye. Similar summaries will be produced for study drug/procedure-related AEs, AEs leading to discontinuation, and SAEs. AEs will also be summarised by maximum severity, relationship to study drug/procedure, and time to onset and resolution.

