4.10 Disposition of Subjects

The number of subjects who sign Informed Consent, who receive study treatment, who complete the study and the reasons for any premature discontinuation from the study will be presented. The number of subjects included in the All Treated Subjects analysis set and the Immunogenicity analysis set will also be presented. For each study visit, the number of subjects who attend the visit will be summarised.

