4.17.10 Adverse Events

Treatment Emergent Adverse Events (TEAEs) are defined as AEs starting on or after the day of the first surgery. AEs reported in subjects who received timrepigene emparvovec treatment in their first eye in an antecedent study will be considered as TEAEs. Where an AE start date is partially or fully missing, and it is unclear as to whether the AE is treatment emergent, it will be assumed that it is. Summary tables will include TEAEs only. TEAEs will be summarised by eye (for ocular events), by period, and overall. Each by-period summary table will be repeated by surgery window instead.

The number and percentage of subjects reporting any event, any non-ocular event, any ocular event, any ocular event in SE1 and any ocular event in SE2 will be summarised. Percentage will be calculated based on the number of subjects in the corresponding period or surgery window or overall. The 95% CI will be calculated using the Clopper-Pearson method.

Overall summary table of TEAE by period (or by surgery window) will be provided for the following categories:

- Number and percentage of subjects with a TEAE
- Number and percentage of subjects with a serious TEAE
- Number and percentage of subjects with a Treatment-related (study drug or study procedure) TEAE
- Number and percentage of subjects with a Treatment-related (study drug or study procedure) serious TEAE
- Number and percentage of subjects with a TEAE leading to death
- Number and percentage of subjects who discontinued due to a TEAE
- Number and percentage of subjects with a TEAE by severity
- Number and percentage of subjects with a TEAE by outcome
- Number and percentage of subjects with a TEAE by action taken

Adverse events will be summarized by period (or by surgery window), and overall. The following summaries of TEAEs will be provided:

- TEAEs by SOC and PT
- TEAEs by PT with percentage $\geq 5\%$
- Treatment-related (study drug or study procedure) TEAEs by SOC and PT
- Study procedure-related TEAEs by SOC and PT
- Study drug-related TEAEs by SOC and PT
- TEAEs by SOC, PT, and maximum severity (missing severity, if any, will be counted as severe).
- Serious TEAEs by SOC and PT
- Treatment-related (study drug or study procedure) serious TEAEs by SOC and PT
- Study procedure-related serious TEAEs by SOC and PT
- Study drug-related serious TEAEs by SOC and PT
- TEAEs leading to death by SOC and PT
- TEAEs reported by subjects who discontinued due to SAE by SOC and PT

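### Second eyes withheld after a first-eye outcome get no reason in the disposition table; separately, the SOC/PT discontinuation table is narrowed to SAEs without being declared

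*SAP*

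**What the plan says.** **Completion.** SAP 3.3, like Protocol 7.1: "A subject is considered to have completed the study if he completes Period 2, Visit 9 (Month 12"). No other route to completion is given.

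**Withholding SE2.** Protocol 8.3 has two rules. One applies when severe ocular inflammation, or another post-operative sequela, that is "unresponsive to treatment occurs in SE1, the second eye should not be treated". The other is at the investigator's discretion, where a persistent complication or "poor visual function outcome presents post-operatively in SE1, the second eye may not be treated". Each is followed by the same instruction: "However, Period 1 should be continued for monitoring of safety for the duration of the study". Protocol 10.2 repeats the first rule. Protocol 11.3 repeats it for inflammation and adds "However, the subject will continue to be followed for safety for the duration of the study".

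**Disposition.** SAP 4.10 reports the numbers who consent, who receive study treatment (not split by eye), and those "who complete the study and the reasons for any premature discontinuation from the study will be presented". It also counts the subjects attending each visit.

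**AEs and discontinuation.** Protocol 13.6.7, after describing the SOC/PT summaries, says: "Similar summaries will be produced for study drug/procedure-related AEs, AEs leading to discontinuation, and SAEs". The last SOC/PT bullet in SAP 4.17.10 is "TEAEs reported by subjects who discontinued due to SAE by SOC and PT". The overall TEAE table in the same section has a row for subjects who discontinued due to any TEAE and one for TEAEs by action taken. SAP 4.20 declares four changes from the protocol: fixation location, sensitivity points, time to AE resolution and LOCF. This one is not among them.

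**The concern.** The study's one objective is the safety of sequential treatment of both eyes. In a two-step regimen, not giving the second step because the first went badly is the nearest equivalent of stopping treatment for an adverse event. A reader of the report will want to know how many subjects were stopped there and why. That number also governs how Period 2 is read: its denominators contain only subjects judged fit to proceed (plus those who entered from an antecedent study), so a Period 2 percentage is conditional on an acceptable first-eye course.

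The SOC/PT table is a separate matter. As worded it would omit every non-serious AE that made a subject leave, and would include events that had nothing to do with leaving.

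**Working it through.** **1. Where a withheld subject appears.** Take a subject treated in SE1 within GEMINI, with SE2 withheld after a first-eye outcome, who attends Period 1 Visit 9.

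| Output | What it shows for him |
|---|---|
| Completed (SAP 3.3, 4.10) | No; impossible without Period 2 Visit 9 |
| Reason for premature discontinuation (SAP 4.10) | None, if the site treats him as still on study, as Protocol 8.3 directs |
| Received study treatment (SAP 4.10) | Yes; not split by eye |
| Attendance (SAP 4.10) | Present through Period 1, absent at Period 2 Visit 1; no reason |
| TEAEs by period and overall (SAP 4.17.10) | First-eye events counted in Period 1 and overall |
| TEAEs by action taken (SAP 4.17.10) | Unknown; categories not defined |
| TEAEs by surgery window (SAP 4.7, 4.17.10) | No category for a subject without second surgery |

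On the last row, the window is the interval between the two treatments. A target interval is set at screening, so he could be placed by target, but the SAP does not say so. Period 1 is also defined to end on the day before second-eye surgery (SAP 4.3), so it has no stated end for him.

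**2. The SOC/PT table under each rule** (hypothetical subjects).

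| Subject | Protocol 13.6.7 | SAP 4.17.10 SOC/PT bullet |
|---|---|---|
| Leaves because of one non-serious AE | 1 event | 0 events |
| Leaves because of one SAE; had two other TEAEs | 1 event | 3 events |
| SE2 withheld, stays on study | 0 events | 0 events |

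The SAP rule is narrower in its trigger and lists different events. The third line shows that restoring the protocol's table would not capture withholding, so the two gaps need separate remedies.

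**3. Eyes.** The plan's figure reproduces: 60 × 2 = 120. SAP 4.3 records 6 subjects whose first eye was treated in an antecedent study. With exactly 60 enrolled, 54 start with SE1 in GEMINI, and at most 54 × 2 + 6 = 114 eyes are treated within it, less one for each SE2 withheld.

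**4. Size.** The documents give no withholding rate, so counts are assumed. Clopper-Pearson (the SAP 4.2 method), n = 54:

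| Withheld | % | 95% CI | Eyes treated in GEMINI |
|---|---|---|---|
| 0 | 0 | 0–6.6 | 114 |
| 1 | 1.9 | 0.05–9.9 | 113 |
| 3 | 5.6 | 1.2–15.4 | 111 |
| 6 | 11.1 | 4.2–22.6 | 108 |

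The chance of at least one case is 1 − (1 − q)^54. For assumed q of 2%, 5% and 10% it is 66%, 94% and more than 99%.

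**5. Conditioning, as illustration only.** Let a share p of subjects have per-eye risk a and the rest risk b, and let a fraction w of those harmed in SE1 be withheld. Then

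Period 2 risk = [p(1 − wa)a + (1 − p)(1 − wb)b] / [p(1 − wa) + (1 − p)(1 − wb)], against pa + (1 − p)b unselected.

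For p = 0.1, a = 0.4, b = 0.05:
- Unselected: 0.04 + 0.045 = 8.5%.
- w = 1: (0.024 + 0.04275)/(0.06 + 0.855) = 0.06675/0.915 = 7.3%.
- w = 0.5: (0.032 + 0.043875)/(0.08 + 0.8775) = 0.075875/0.9575 = 7.9%.

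For p = 0.2 with the same a and b:
- Unselected: 0.08 + 0.04 = 12.0%.
- w = 1: 0.086/0.88 = 9.8%.
- w = 0.5: 0.103/0.94 = 11.0%.

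**The case against.** Four stronger readings are tempting, and the documents do not support them.

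- *Withholding is counted nowhere.* Period 2 Visit 1 is the SE2 injection visit and attendance is counted at each visit. AE percentages use the number of subjects in the period, so the drop is visible. Nor is the harm lost: these subjects stay in the All Treated Subjects set, and their first-eye events, including ocular inflammation, reduced acuity and letter losses, enter the Period 1 tables. The action-taken row might even identify withholding, depending on an eCRF we cannot see. What is missing is the reason.
- *Discontinuation is now counted only for SAEs.* The overall TEAE table still counts subjects who discontinued due to any TEAE. Only the SOC/PT breakdown is narrowed.
- *The 4/79 (5.1%) in Protocol 5.4 gives the rate.* It is the frequency of serious reduced visual acuity, not of withholding. Applying it to 54 subjects (about 2.7) would borrow a number for a different event.
- *Period 2 rates will be biased by a known amount.* The prone shares and risks above are invented. Withholding every harmed subject (w = 1) is not the protocol's rule: withholding for a poor outcome is discretionary, and resolved events permit Period 2. The gaps are also small beside the imprecision: 4 of 54 (7.4%) has a 95% CI of 2.1–17.9%.

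It can also be said that Protocol 8.3 puts the withholding rules under its withdrawal criteria, beneath an *other* reason to be specified on the eCRF. A site might therefore finally record such a subject as discontinued, with a reason. That is possible. It would mean the same event is classified differently between sites, which is itself a reason to define his status.

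Finally, widening the definition of completion would be a doubtful remedy. Someone denied the second eye because of harm would become a completer of a bilateral study, and the rule also stands in the protocol.

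**Conclusion.** Two modest gaps stand. First, a subject stopped between the eyes because of a first-eye outcome cannot complete and need not appear as discontinued, and no planned output gives the reason SE2 was not treated. His absence can only be inferred from attendance and denominators. This rests on the instruction that he stays on study and on the absence of a defined action-taken category. Second, the SOC/PT discontinuation table selects a different set of events from the one the protocol planned, and the change is undeclared. This follows from the wording alone.

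The size of the first gap cannot be taken from the documents. On assumed counts of 1 to 6 among 54 it concerns 1.9% to 11.1% of subjects, and the conditioning figures show only the direction of a possible effect. The clinical withholding rule is not in question here.

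**What to change.** (a) In SAP 4.17.10, replace the last SOC/PT bullet with *TEAEs leading to study discontinuation, by SOC and PT*, serious or not. List separately the TEAEs recorded as the reason SE2 was not treated. If the narrower table is kept, declare it in 4.20.

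(b) In SAP 4.10, among subjects treated in SE1 within GEMINI, add SE2 treated and SE2 not treated, the latter by reason: first-eye AE or sequela, poor visual outcome, eligibility committee decision, subject choice, other. Give a Clopper-Pearson interval. Footnote the Period 2 tables with the number who did not proceed.

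(c) Keep the completion definition, but report *followed to Period 1 Visit 9, SE2 not treated* as its own category. Give these subjects a *no second surgery* column in the by-surgery-window TEAE tables.

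The cost is SAP wording, a few table rows and possibly one data field. The Version 5.0 summary of changes says signed surgery authorisation forms are kept in the Trial Master File, but the documents do not say that reasons for not proceeding are held in the database.
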